1.2 Secondary Objectives

- **1.2.1** To assess the safety and tolerability of entinostat plus nivolumab in patients with unresectable or metastatic cholangiocarcinoma and unresectable or metastatic pancreatic adenocarcinoma.
- **1.2.2** To assess the progression free survival (PFS) status of patients with unresectable or metastatic cholangiocarcinoma and unresectable or metastatic pancreatic adenocarcinoma treated with entinostat plus nivolumab at 6, 12 and 24 months.
- **1.2.3** To determine the overall survival (OS) status of subjects with unresectable or metastatic cholangiocarcinoma and unresectable or metastatic pancreatic adenocarcinoma treated with entinostat plus nivolumab.
- **1.2.4** To determine the overall survival (OS) status of subjects with unresectable or metastatic cholangiocarcinoma and unresectable or metastatic pancreatic adenocarcinoma treated with entinostat plus nivolumab at 6 months, at 1, 2 and 3 years.
- **1.2.5** To assess the duration of response among subjects who demonstrate an objective response to treatment with entinostat in combination with nivolumab.

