4.10 Duration of Follow Up

The Follow-Up Phase begins when the decision to discontinue a subject from study therapy is made (no further treatment with study therapy).

All subjects who discontinue investigational product should comply with protocol specified follow-up procedures as outlined in Section 10, Study Calendar.

A mandatory End of treatment (EOT) visit (+/- 7 days) should be performed 28 days after the last dose of study drug(s).

After completion of the EOT visit, subjects will be followed every 3 months for survival.

Subjects who are discontinued from the study treatment due to an unacceptable toxicity will be monitored for safety until the resolution of the AE to \leq grade 1 or stabilization or until initiation of a new therapy for their cancer, whichever occurs first.

SAEs will be collected and recorded throughout the study period, from the first dose of the investigational agent through 100 days (+ 14 days) after the last dose of study drug or end of the study (if thought to be related to study drug), or 30 days after the initiation of a new anticancer therapy, whichever is earlier.

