PET-CT: At present, the low dose or attenuation correction CT portion of a combined PET-CT is not always of optimal diagnostic CT quality for use with RECIST measurements. However, if the site can document that the CT performed as part of a PET-CT is of identical diagnostic quality to a diagnostic CT (with IV and oral contrast), then the CT portion of the PET-CT can be used for RECIST measurements and can be used interchangeably with conventional CT in accurately measuring cancer lesions over time. Note, however, that the PET portion of the CT introduces

additional data which may bias an investigator if it is not routinely or serially performed. Further, if the subject is allergic to contrast dye, the case should be discussed with the IND Sponsor.

Ultrasound: Ultrasound is not useful in assessment of lesion size and should not be used as a method of measurement. If new lesions are identified by ultrasound in the course of the study, confirmation by CT or MRI is advised. If there is concern about radiation exposure at CT, MRI may be used instead of CT in selected instances.

Endoscopy, Laparoscopy: The utilization of these techniques for objective tumor evaluation is not advised.

Tumor markers (CA 19-9): Tumor markers alone cannot be used to assess response. If markers are initially above the upper normal limit, they must normalize for a subject to be considered in complete clinical response.

Cytology: The cytological confirmation of the neoplastic origin of any effusion that appears or worsens during treatment when the measurable tumor has met criteria for response or stable disease is mandatory to differentiate between response or stable disease (an effusion may be a side effect of the treatment) and progressive disease.

FDG-PET: While FDG-PET response assessments need additional study, it is sometimes reasonable to incorporate the use of FDG-PET scanning to complement CT scanning in assessment of progression (particularly possible 'new' disease). New lesions on the basis of FDG-PET imaging can be identified according to the following algorithm:

- Negative FDG-PET at baseline, with a positive FDG-PET at follow-up is a sign of PD based on a new lesion.

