8.3.6 Progression-Free Survival

Progression-free survival (PFS) is defined as the duration of time from start of treatment to time of progression per RECIST1.1 or death whichever comes first. PFS for patients who are not progressed at the time of data analysis will be censored on the date of the latest tumor assessment. Patients who go off treatment and begin alternate therapy, prior to progressing on this protocol will be censored at the time on the date of the latest tumor assessment before starting the alternate therapy. We assume that all patients have radiographic scans during screening period and before starting treatment. The following table describes how PFS event is defined and PFS time is calculated. Only radiographic scans used to tumor assessment per RECIST 1.1 before starting the alternate therapy will be counted if patients go off treatment and begin alternate therapy. The following table shows how PFS is defined in various scenarios (*Table 8.3.2*).

Scenario	PFS event (1) or censor (0)	PFS time
At least one post treatment scan is available and tumor response is evaluated according to RECIST 1.1 and all scans are completed on the schedule or off the schedule within a month and patient is alive at the latest follow-up.	1 if PD 0 if no PD	The date of the latest tumor assessment – the date of starting treatment

Table 8.3.2 Definition of PFS

At least one post treatment scan is available and tumor response is evaluated according to RECIST 1.1, but the gap between radiographic scans is greater than 3 months. No PD is observed on the latest scan before the gap occurs.	0	The date of the latest tumor assessment before the gap– the date of starting treatment
No disease progression per RECIST 1.1 is observed on the post-treatment scans and patient dies before the next scheduled scan + 1 month.	1	The date of death – the date of starting treatment
No disease progression per RECIST 1.1 is observed on the post-treatment scans and patient dies. The period from the latest scan to death is greater than 3 months.	0	The date of the latest tumor assessment – the date of starting treatment
No post-treatment scan is available and patient dies before the first scheduled scan + 1 month.	1	The date of death – the date of starting treatment
No post-treatment scan is available and patient is lost follow up or patient dies >3 months later after starting treatment.	0	0

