NOTE: If applicable, the daily dose of entinostat may occur prior to hematology/chemistry tests and these laboratory tests may be drawn at the same time as the correlative blood samples.

- ^{19.} A third mandatory biopsy will be performed at week 6 from Cycle 1, Day1. A window of +14 days applies to this time point
- ^{20.} An optional biopsy will be performed at the time of disease progression.
- ^{21.} Archival tumor specimens from previously collected samples will be obtained for correlative analysis, if available.
- ^{22.} Weekly assessments for toxicity/adverse events may occur by phone on days when entinostat alone is administered. Additionally, assessments are to continue for 30 days after the last dose of nivolumab (at intervals <21 days) or to resolution of drug-related AEs to \leq Grade 1, whichever occurs later. SAEs that occur within 100 days of the last treatment or before initiation of a new antineoplastic treatment should also be followed and recorded. These may occur by phone for subjects no longer being seen at the institution; however, an in-person clinic visit may be needed to confirm event resolution and/or to effectively evaluate possible immune-related events. Subjects must be told of follow-up requirements at study entry.
- ^{23.} Subjects who complete or discontinue from treatment because of progression disease will be followed (by phone or email) every three months (+/- 2 weeks) after completion of the EOT visit for up to 2 years or study closure to monitor overall survival. Information of other cancer therapies after discontinuation from the study treatment will also be collected.

For subjects who discontinue treatment for reasons other than tumor progression, will be contacted (by phone or email) every three months (+/- 2 weeks) after completion of the EOT for up to 2 years or study closure to monitor overall survival, and information

93

about disease status will be also collected if possible (i.e. radiological imaging and/or tumor markers) until documented tumor progression.

NOTE: For evaluation of PFS, all subjects who discontinue study drug administration prior to 6 months must have restaging scans/imaging within a 7 day window of the 6 month time point from the date of initiation of combination treatment

J1798/Version 5.0/May 21, 2020

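### The mandatory 6-month off-treatment scan covers subjects in whom it cannot count, required imaging is missing for those who stop without progression, and Table 8.3.2 can discard the scan's result

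*Combined protocol and SAP*

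**What the plan says.** Section 4.10 places an end-of-treatment (EOT) visit 28 days after the last dose. It then states: "After completion of the EOT visit, subjects will be followed every 3 months for survival". It refers to Section 10 for the follow-up procedures.

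Footnote 23 in Section 10 supplies the detail:

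- "For subjects who discontinue treatment for reasons other than tumor progression, will be contacted (by phone or email) every three months", for up to 2 years or until study closure. For these subjects information "about disease status will be also collected if possible (i.e. radiological imaging and/or tumor markers) until documented tumor progression". No imaging interval is given.
- A closing note, stated to be for evaluation of PFS, says "all subjects who discontinue study drug administration prior to 6 months must have restaging scans/imaging". The scan is due no more than 7 days from month 6, counted from the start of combination treatment.

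Footnote 2 sets disease assessments every 8 weeks (±1 week) from Cycle 1 Day 1 for 6 months. After that the interval may be extended to every 12 weeks (±1 week). It does not say that this continues once treatment stops.

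Objective 1.2.2 asks for PFS status in patients "treated with entinostat plus nivolumab at 6, 12 and 24 months", and objective 1.2.5 asks for duration of response (DOR). Section 12.3.2 plans Kaplan-Meier estimates for both.

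Section 8.3.6 adds, for subjects who begin alternate therapy: "Only radiographic scans used to tumor assessment per RECIST 1.1 before starting the alternate therapy will be counted". In Table 8.3.2, a gap of more than 3 months between scans leads to censoring at the last scan before the gap. A death more than 3 months after the last scan is also censored.

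**The concern.** A scan required for PFS should be required where it can change PFS, and the PFS rules should then use it. Neither holds here.

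The note covers everyone who stops before month 6. For a subject who has already progressed, Sections 4.9 and 12.3.2 date progression to the first RECIST event, so a later scan changes nothing. For a subject on alternate therapy, Section 8.3.6 does not count the scan.

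The subjects in whom off-treatment imaging does matter are those who stop without progression, for example for toxicity (Section 4.8). After month 6 no scan is required of them, although PFS is to be read at months 12 and 24 and DOR runs to objective progression or death. Section 8.3.5 censors DOR at the last assessment that the protocol specifies, so it is unclear whether an optional later scan would even extend follow-up.

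For some who stop early, the mandated scan arrives after a gap long enough for Table 8.3.2 to set its result aside.

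**Working it through.** **1. The plan's own figures.** Section 12.2 gives design figures for ORR only. Early stopping at a 5% ORR is 0.95^13 = 0.513 (stated 51%). The rejection probability is the sum over x = 1 to 13 of b(13, x, p) × P(Bin(14, p) ≥ max(0, 4 − x)). It is 0.0416 at p = 0.05 (stated limit 5%) and 0.801 at p = 0.20 (stated 80%). The figures reproduce. No precision is stated for PFS or DOR, so there is nothing to reproduce for the endpoints at issue.

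**2. Units.** Weeks are counted from Cycle 1 Day 1.
- 3 months = 3 × 365.25 / 12 / 7 = 13.0 weeks
- 6 months = 26.1 weeks
- 12 months = 52.2 weeks

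**3. Required scans after stopping, beyond any EOT scan.**

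| Status | Stops before month 6 | Stops after month 6 |
|---|---|---|
| Already progressed | 1, cannot change PFS | 0 |
| On alternate therapy | 1, not counted | 0 |
| No progression, no new therapy | 1, then none | 0 |

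The EOT scan is itself uncertain. The calendar's EOT imaging cell points to footnote 20, which concerns the optional biopsy at progression.

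**4. Gap before the 6-month scan.** Take a subject who stops at week 6. A footnote 2 scan falls due at week 8, and EOT is at week 6 + 4 = 10. Gap = 26.1 − last scan, and the 7-day window on the 6-month scan moves it by ±1 week.

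| Last scan | Gap (weeks) | With window | Against 13.0 weeks |
|---|---|---|---|
| Week 8 | 18.1 | 17.1 to 19.1 | Over: censored at week 8 |
| Week 10 (EOT) | 16.1 | 15.1 to 17.1 | Over: censored at week 10 |
| Week 16 | 10.1 | 9.1 to 11.1 | Within: the scan counts |

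The dividing line is a last scan at about 26.1 − 13.0 = week 13. Before that, and with no optional scan in between, the mandated scan cannot contribute a PFS event.

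**5. After month 6.** From month 6 to month 12 is 52.2 − 26.1 = 26.1 weeks, twice the 3-month limit, with no required scan off treatment. On footnote 2's 12-weekly interval, counted from a week-24 scan, scans would fall at weeks 36 and 48 before month 12, and at weeks 60, 72, 84 and 96 before month 24.

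**6. Longest interval that footnote 2 allows.** 12 + 1 + 1 = 14 weeks, against a limit of 13.0. A subject scanned within the schedule can therefore still trip the gap rule.

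**7. Size.** Each subject is 1/27 = 3.7 percentage points of a cohort. The documents give no rate of stopping without progression. If 1 to 6 subjects per cohort did so (an assumption), 3.7 to 22.2 points of the cohort would lack required imaging at months 12 and 24. These are shares of the cohort, not estimates of bias. At the success threshold of 4 responders, one such responder is 1/4 = 25% of the DOR data.

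**The case against.** The best defence is that continued imaging is plainly intended. Section 8.2.2 sets 8-weekly scans without limiting them to treatment. Footnote 2 counts from Cycle 1 Day 1, not from dosing. Footnote 23 seeks disease status up to progression. Section 8.3.3 urges every effort to document progression after symptomatic deterioration. That shows intent, and it means the defect is a missing requirement and interval, not the absence of any plan. It does not supply the requirement. Section 4.10 defers to Section 10; the only clause that expressly keeps scans going (Section 5) covers dosing delays; and the 6-month note would be unnecessary if scheduled scans continued off treatment.

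It can also be said that the note follows the paragraph on stopping for reasons other than progression and was meant for that group. That may be so, but its words cover all subjects.

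The censoring in the week-6 example is conditional, since an optional scan could intervene. The first 3-monthly contact after a week-10 EOT falls near week 23, so a scan taken then would itself sit at the 3-month limit.

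Four stronger readings are tempting and not supported:

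- **Subjects who stop early have no required imaging.** They have the 6-month scan.
- **Footnote 23 lets tumor markers define progression.** It lists markers as information to collect. PFS requires RECIST 1.1 (Sections 8.3.6 and 12.3.2), and DOR requires objectively documented progression (Section 8.3.5). The statement "Tumor markers alone cannot be used to assess response" in Section 8.2.2 concerns response. No deletion is needed.
- **PFS and DOR are overstated.** Late detection can lengthen PFS. Censoring loses information and biases PFS only if those censored differ in prognosis from those still followed. For DOR the direction is uncertain.
- **Most mandated scans are wasted.** The documents do not say what share of early stoppers will have progressed.

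**Conclusion.** The point holds. The mandatory scan includes subjects in whom it cannot affect PFS. Required imaging ends at month 6, or at EOT for later stops, in subjects whose PFS and DOR are still open. Footnote 23 and Table 8.3.2 contradict each other for a subject who stops near week 6: the gap is 16 to 18 weeks against a limit of 13.0, so progression on the scan mandated for PFS is not counted. That last result assumes that no optional scan intervenes.

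The number of subjects affected and the net bias cannot be derived from the documents. PFS and DOR are secondary and descriptive, and the primary ORR is unaffected. The change should be made, but the trial's main conclusion does not depend on it.

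**What to change.** 1. In footnote 23, limit the mandatory 6-month scan to subjects without RECIST 1.1 progression who have not started new anticancer therapy.
2. State that subjects who stop treatment without progression continue imaging on the footnote 2 schedule until progression, new anticancer therapy, death or withdrawal. Leave unchanged the repeat scans for treatment beyond progression (Sections 8.3.3 and 12.3.2).
3. Amend Table 8.3.2 so that progression first seen on the mandated 6-month scan counts as a PFS event, and set the gap limit above the longest interval the schedule allows (14 weeks). Add a sensitivity analysis under the current gap-censoring rule.

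The cost is an amendment to one footnote and one table, plus a few scans in subjects who stop without progression. Scans dropped in subjects already progressed offset this, by an amount the documents do not allow us to state. Some progressions will still be dated late when first seen after a long interval; the sensitivity analysis shows how much that matters. Sample size, type I error and power do not change.

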11. DATA REPORTING / REGULATORY REQUIREMENTS

Adverse event lists, guidelines, and instructions for AE reporting can be found in **Section 6** (Adverse Events: List and Reporting Requirements).

11.1 Data Management

All information will be collected on study-specific case report forms (CRFs) by study staff. These data will be reviewed for completeness and accuracy by the PI.

CRFs will be used to capture study results and data. The study coordinator or other authorized study personnel will transcribe data from source documents onto eCRFs. Before or between visits, the IND Sponsor,, Syndax and BMS or designee may request copies of the CRFs for preliminary medical review. Once the CRFs are complete and source-verified, the investigator must sign and date all required pages, verifying the accuracy of all data contained within the CRF. Training will be provided on proper completion of CRFs.

11.2 Data Confidentiality and Subject Anonymity

All information about the nature of the proposed investigation (with the exception of information required by law or regulations to be disclosed to the IRB, the subject or the appropriate regulatory authority) must be kept in confidence by the entire study personnel.

The anonymity of participating subjects must be maintained. Subjects will be identified by their initials and an assigned subject number on CRFs and other documents retrieved from the site or sent to the IND Sponsor, Syndax and BMS, study monitor, regulatory agencies, or central laboratories/reviewers. Documents that identify the subject (e.g., the signed ICF) must be maintained in strict confidence by the investigator, except to the extent necessary to allow auditing by the appropriate regulatory authority, the study monitor, IND Sponsor or their representative.

11.3 Protocol Compliance

Substantive changes in the protocol include changes that affect the safety of subjects or changes that alter the scope of the investigation, the scientific quality of the study, the experimental design, dosages, assessment variable(s), the number of subjects treated or the subject selection criteria.

A protocol amendment must receive IRB approval before implementation. In parallel with the IRB approval process, the protocol amendment will be submitted to the appropriate regulatory authority as an amendment to the regulatory submission under which the study is being conducted. If a protocol amendment requires changes in the ICF, the revised ICF and protocol prepared by the investigator must also be approved by the IND Sponsor, Syndax/BMS, and the IRB before implementation.

Emergency departures from the protocol that eliminate an apparent immediate hazard to a particular subject and that are deemed crucial for the safety and well-being of that subject may be instituted for that subject only. The investigator or the attending physician also will contact the IND Sponsor and/or designee as soon as possible in the case of such a departure. These departures do not require preapproval by the IRB; however, the IRB and the IND Sponsor and/ or designee must be notified in writing as soon as possible after the departure has been made. In addition, the investigator will document in the subject's CRF the reasons for the protocol deviation and the ensuing events.

11.4 Safety meetings

Scheduled meetings will take place weekly and will include the protocol PI, study coordinator(s), research nurse (s), and sub-investigators (as appropriate). During these meetings matters related to the following will be discussed: safety of protocol participants, validity and integrity of the data, enrollment rate relative to expectation, characteristics of participants, retention of participants, adherence to protocol (potential or real protocol violations), data completeness, and progress of data for objectives.

Quarterly teleconferences will be scheduled to include the Investigator and Syndax and BMS representatives. During these meetings, the Investigator shall provide Syndax and BMS with study progress updates. The Investigator will provide a summary of key points from the weekly meetings with a focus on safety of the protocol participants, enrollment status, and progress of data for objectives. In addition, both Syndax and BMS will provide safety and applicable program updates to the Sponsor.

11.5 Monitoring

The SKCCC Compliance Monitoring Program will provide external monitoring for JHU-affiliated sites in accordance with SKCCC DSMP (Version 6.0, 02/21/2019). The SMC Subcommittee will determine the level of patient safety risk and level/frequency of monitoring.

[name] [name] will be holding the IND for this study. She will comply with all regulated reporting requirements to the FDA.

12. STATISTICAL CONSIDERATIONS

12.1 Overall Study Design

This is an open-label, two-stage, phase 2 study evaluating the clinical activity and safety of entinostat plus nivolumab. We will enroll two cohorts of patients: unresectable or metastatic cholangiocarcinoma (Cohort 1) and unresectable or metastatic pancreatic adenocarcinoma (Cohort 2). Patients must have progressed (or were intolerant) to 1 or 2 prior chemotherapy regimens in the metastatic setting, or progression < 6 months from the completion of adjuvant chemotherapy.

The primary objective of the trial is to determine whether the combination of entinostat plus nivolumab yields a clinically compelling antitumor activity measured as objective response rate (ORR, assessed by RECIST 1.1). Secondary endpoints include safety, progression-free survival (PFS), overall survival (OS), and immunologic correlates.

The study is planned with 27 evaluable subjects per histology, based on a two-stage design that allows early termination for lack of efficacy.

